5.2 Secondary Outcomes

The following secondary outcomes will be measured at each timepoint (at baseline and 6 weeks, 3 months and 1 year after surgery):

Range of motion

Flexion and extension of the MCP and thumb Interphalangeal (IP) joint will be measured with a goniometer. The evaluation of active thumb opposition is based on the Kapandji index, ranging from 1 to 10 [8]. Patients try to touch their fingers with the tip of the thumb. The score is 1 when patients are able to touch only the lateral side of the index finger and 10 when they can reach the volar crease of the hand.

Grip strength and key pinch

Grip strength of the affected hand will be measured with the help of a JAMAR dynamometer. Thumb key pinch will be measured with a pinch gauge. The testing position is standardized as recommended by the American Society of Hand Therapists [30].

The brief Michigan Hand Outcomes Questionnaire (MHQ)

The brief MHQ measures hand function and shows good measurement properties [7, 31]. The score ranges from 0 to 100 with higher scores indicating better hand function. We will use the German version of the brief MHQ [32].

Pain

The pain level of the thumb at rest and during daily activities will be documented using a Numeric Rating Scale (NRS; 0 = no pain, 10 = worst pain).

Satisfaction

At follow-up, there will be three additional questions about satisfaction:

- How is your operated thumb in general compared to before the surgery?
 - Response options: Much better (score 5), slightly better (score 4), unchanged (score 3), slightly worse (score 2), much worse (score 1)
- How satisfied are you with the treatment result of the operation on your thumb?
 - Response options: Very satisfied (score 5) / satisfied (score 4) / neither satisfied nor dissatisfied (score 3) / dissatisfied (score 2) / very dissatisfied (score 1)

- In hindsight, would you decide to have this operation again?
 - Response options: No (score 1), Not sure (score 2), Yes (score 3)

Physical work demands

To estimate the physically demanding work, the patients will be asked about their physical activity during work as well as the presence of strenuous work [9].

- Do you have to use your hands a lot during your regular work?
 - Response options: Yes / No
- Do you regularly have to carry / hold loads with your hand or work using the strength of your hands?
 - o Response options: No / A little / Sometimes / A lot
- Do you have to perform repetitive hand movements during your work (e.g. repeatedly grasping something, turning something, typing, etc.)?
 - Response options: No / Seldomly / Sometimes / Often

5.3 Other Outcomes of Interest

Radiographs

Preoperatively, OA severity is graded from stage I (normal articular contours with joint widening due to ligament laxity) to stage IV (complete thumb CMC joint deterioration and narrowed, sclerotic scaphotrapezial joint) based on the Eaton classification [33].

At follow-up, the radiographs are analysed for implant fracture, migration, luxation, radiolucent lines, cysts, fractures, bone reactions and peritendinous calcification.

5.4 Safety Outcomes

Adverse events that had been occurred during or after primary and revision surgery will be extracted out of the medical records and patients will be asked about additional events not documented in the medical records.

6 STUDY DESIGN

6.1 General study design and justification of design

This study will be a prospective mono-center cohort study. The data collection period from first patient visit (FPFV) to last patient last visit (LPLV) will be 3.5 years. Including study preparation and writing of the final report the study will last 5 years. Patients with primary osteoarthritis (OA) at the thumb carpometacarpal (CMC I) joint who will be operated with a Touch® prosthesis and who are working will be included. Patients with a revision surgery, rheumatoid arthritis or non-working patients will be excluded. As comparison group, we will use the data of a previous cohort of patients who had a RSI arthroplasty and were working (n=42) [4].

The project will start in Q1/2021 and includes the following milestones:

Milestones	Expected completion
Preparation of project documents	Q4.2020/Q1.2021
Submission to Ethics Committee	Q1.2021
Recruitment and data collection	Q1.2021-Q3.2024
Submission of publication	Q1.2025

7 STUDY POPULATION

7.1 Eligibility criteria

Participants fulfilling all of the following inclusion criteria are eligible for the study:

- Informed Consent as documented by signature (Appendix Informed Consent Form)
- Patient is diagnosed with primary osteoarthritis (OA) at the thumb carpometacarpal (CMC I) joint and will be operated with a Touch® prosthesis
- Patient is working in Switzerland and intends to continue doing so for at least the duration of their study participation (1 year)
 - Comparison group: Patients who received a resection arthroplasty in a previous study (KEK-ZH Nr. 2013-0381) and had an occupation at that time

The presence of any one of the following exclusion criteria will lead to exclusion of the participant:

- Patient with any type of revision surgery at the CMC I joint
- Patient with rheumatoid arthritis
- Patient has an additional surgery in the same session (except for simultaneous trigger finger release at the thumb)
- Non-working patients
- Legal incompetence
- German or English language barrier which prevents the study participant from completing the questionnaires

7.2 Recruitment and screening

The study will take place in the department of hand surgery of the Schulthess Klinik, Zurich, Switzerland. Potentially eligible patients will be identified by the surgeons during the pre-operative consultation and informed of the study. After the examination by the surgeon, the eligible patient will be contacted by the study assistant either on site or by phone. They will receive more detailed information about the purpose and the processes of the project and asked for their willingness to participate. If they are willing, they will receive the study information sheet and consent form on site or via mail. The patient will be given ample time to decide whether to participate in the study or not and once determined to participate will sign the informed consent form. The patient will now be included in the study. Patients have the right to withdraw their consent at any time without any consequences regarding their medical care and clinical follow-up.

7.3 Assignment to study groups

All patients who fulfil the inclusion criteria will be considered for the study. Since this study utilises data of a previous study for the comparison group all the recruited participants will be assigned to the intervention group.

7.4 Criteria for withdrawal / discontinuation of participants

Each patient has the right to withdraw from the project at any time without consequences. If a patient withdraws from the project, the reason(s) will be documented. Data collected so far will be analysed and stored in encoded form.

All patients who withdraw from the project will still be clinically followed up according to the standard care in the Schulthess Klinik, in case the patient agrees with this procedure.

8 STUDY INTERVENTION

8.1 Identity of Investigational Products

8.1.1 Experimental Intervention

The patient questionnaires (work situation, WPAI, brief MHQ, EQ-5D-5L, complications, expectations) are the only investigational product. The operation with the Touch® Dual mobility trapeziometacarpal implant is a routinely performed and accepted surgical procedure which will not be focus of this study. Usually, the clinical examinations are done by the study assistant right before surgery and by the surgeon at the follow-up consultations. Due to organisational aspects and to reduce risk of bias, the preoperative assessment will be done by the study assistant right after the preoperative consultation. Parts of the clinical examination at follow-up will also be done by the study assistant instead of the surgeon.

8.1.2 Control intervention

The control group was studied in a previously submitted but not yet published study [10] and the outcome data will be used in this study for the sake of comparison. The only data still to be collected for this group will be the cost data.

8.2 Compliance with study intervention

Post-surgery the patients will schedule their first two follow-ups. This will be done by the surgeon's secretary office. A study assistant will make sure the patients are invited again for the later 1-year follow-up and will schedule the visit during the follow-up range.

A patient is non-compliant if he/she either doesn't fill out the questionnaires or doesn't show up for the clinical examinations. Non-compliance and the reason thereof will be documented electronically. The study assistant will follow up on non-compliant patients if some or all of the questions on a questionnaire weren't filled out or if the patient doesn't show up for the examinations. If the participant does not want to participate in the study anymore, he will be documented as a dropout. If the participant didn't fill out the questionnaires at the right time or for some reason couldn't come for the examination but still wants to participate in the study, we will report his data as missing for a single timepoint.

8.3 Data collection and Follow-up for withdrawn participants

All patients who withdraw from the project will still be clinically followed up according to the standard care in the Schulthess Klinik, in case the patient agrees with this procedure, but will drop out of the study. They will be further documented in our internal DSG-Register.

9 STUDY ASSESSMENTS

9.1 Table of study procedures and assessments

				Follow-up time	points and range	S
	Screening/Baseline (Study start)	Surgery	6 weeks 42 days (±7)	3 months 91 days (± 14)	6 months 182 days (± 21) ¹	1 year 365 days (± 30)
Patient groups	Touch® group	Touch® group	Touch® group	Touch® group	Touch® group	Touch® group
Patient Information / Informed Consent	X					
Demographics	Х					
Diagnosis / Pre-treatment	X					
Surgery / hospital stay		х				
Radiology	X	x	х	x	2	х
Clinical examination Range of motion Kapandji index Grip Strength Key pinch test	x		x	×		x
Patient questionnaires Work status / salary ¹ WPAI ¹ Functional outcomes EuroQoL EQ-5D-5L Satisfaction (after surgery) Pain score Physical work demands	×		x	×	x	x
Complications / AEs		х	х	x	х	x
Direct medical costs		x	x	x	x	x

¹ The work status/salary and WPAI questionnaires as well as the direct medical costs are evaluated solely because of this study. The same goes for all the items (patient questionnaires, complications/AE, direct medical costs) listed under the 6-month follow-up timepoint. Everything else is standard procedure at the clinic.

9.1.1 Assessments of safety outcomes

9.1.1.1 Adverse events

At each follow-up, the investigator will assess whether any AE has occurred. Patients will also be encouraged to report spontaneously AEs occurring at any other time during the study. All AEs, reported by the patient or observed by the investigator, will be documented electronically in the Adverse event / complication form [29], whether or not the investigator concludes the event to be related to the treatment.

Recording about AEs will include at minimum:

- Type and date/onset of event
- Patient identification
- Investigator's name
- Date of implantation of the device
- Short description of the event
- · Event seriousness und possible relation to the investigational device
- The most likely causative factor
- Event treatment or salvage procedure
- Event outcome

The responsible investigator will immediately inform the study coordinator and sponsor about the occurrence of Adverse event / complication, where each event will be classified as serious or non-serious adverse event, as well as its relation to the surgical treatment (none, possible, definite). Final classification of a recorded event as "serious" and/or "device-related" AE will be performed by the respective investigator.

A final evaluation and classification of all AEs will be performed regarding severity after the end of follow-up time by respective investigators.

The severity of all complications will be defined as follows:

- Mild: Transient or mild discomfort (< 48 hours); no medical intervention/therapy required
- Moderate: Mild to moderate limitation in activity, some assistance may be needed; no or minimal medical intervention/therapy required
- Severe: Marked limitation in activity, some assistance usually required; medical intervention/therapy required, hospitalizations possible

9.1.2 Assessments in participants who prematurely stop the study

Each patient has the right to withdraw from the project at any time without consequences. If a patient withdraws from the project, the reason(s) will be documented. Data collected so far will be analysed and stored in encoded form. All patients who withdraw from the project will still be clinically followed up according to the standard care in the Schulthess Klinik, in case the patient agrees with this procedure. They will be further documented in our internal DSG-Register.

9.2 Procedures at each visit

9.2.1 Screening

Potential study patients are identified during preoperative consultation with the doctor and checked for inclusion and exclusion criteria to decide if a patient can participate in the study. Eligible patients are informed about the study by the surgeon and study assistant. Before any study-specific examinations are performed, the patient gives written informed consent to participate in the study according to the CIP. The signed informed consent form is placed into the trial master file. A copy of the informed consent form is handed over to the patient. The patients' participation in the study will also be marked in their respective electronical record (inesKIS).

9.2.2 Baseline

Demographics, medical history and information about the hand condition are obtained. The patient questionnaires (work situation, WPAI, brief MHQ, EQ-5D-5L, complications, expectations) are completed directly online (eCRFs) or on paper CRFs before surgery. Before surgery, the patients will also be clinically examined (range of motion, muscle strength, Kapandji-index, key pinch strength, grip strength). This is usually done by the surgeon during the preoperative consultation as well as shortly before the operation by a study assistant. Since right after the consultation the study assistant will inform the patients about the study in more detail anyways, she will also already clinically examine the patients. As the operations are typically scheduled in the following 2 months, there is thus no need for an additional clinical examination right before the operation. In the rare occasion a patient can't be operated in the next two months, the patient will again be clinically examined shortly before the surgery so as to keep the data up to date. Data will be electronically entered into eCRFs. The twofold measurement of clinical patient data is routinely done in our clinic, reduces the measuring bias of the surgeons and allows for more complete data sets.

9.2.3 Surgery

The surgery and details about the hospitalisation will be documented. Any intraoperative AEs will be documented and reported. The next two visits will be scheduled after the surgery, regardless of the discharge date.

9.2.4 Follow-Ups (6 weeks - 1 year)

For the follow-ups, a questionnaire will be sent to the patient approximately a week before the appointment either via email as a survey or in paper form. The questionnaires will contain questions about the work situation, the WPAI, the brief MHQ, EQ-5D-5DL, and the satisfaction with the surgery. Radiographic images will be taken before the patients meet with the clinician. The study assistant will undertake the clinical examination in which he/she will record the range of motion, grip strength, key pinch strength and the Kapandji index and document them electronically.

9.2.5 Unscheduled visits

Unscheduled visits can take place at any time during the study if a medical emergency occurs or if the surgeon considers this to be appropriate for patient care. Any occurring adverse event is documented directly online into eCRFs.

10 STATISTICAL METHODS

10.1 Hypothesis

Ho: Null hypothesis

The CMC I arthroplasty using the Touch® implant is not more cost-effective compared to the RSI arthroplasty in terms of an acceptable ICER.

H1: Alternative Hypothesis

The CMC I arthroplasty using the Touch® implant is more cost-effective than the RSI arthroplasty in terms of an acceptable ICER.

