3 BACKGROUND AND RATIONALE

3.1 Background and Rationale

In recent years, economic evaluations have become increasingly important because of the growing emphasis on cost containment. The evaluation of both costs and benefits allows more comprehensive consideration of the value of a particular intervention.

In cost-utility studies, benefits are measured in healthy year equivalents, usually expressed by qualityadjusted life-years (QALYs) and the incremental cost-effectiveness ratio (ICER) [1, 2]. The ICER is the difference in costs between two interventions, divided by the difference in their effect expressed in QALYs. There is no explicit threshold defining a cost-effective intervention. Thresholds have been suggested being below 50'000 USD - 150'000 USD for high-income countries [2, 11]. In addition to direct healthcare expenses, the costs associated with loss of productivity lead to substantial economic consequences for the patient, the employer, and society. Studies have shown, that costs associated with loss of productivity are considerably higher than direct medical costs [3]. Here, we see a great potential of the Touch® implant. A first analysis of our registry data showed that in average patients return to work 20 days after surgery. In contrast, data of a previous study investigating loss of productivity in patients after resection-suspension-interposition (RSI) arthroplasty showed a considerably longer absence from work of 54 days [4]. The difference in the return to work is also confirmed by other studies that even showed considerably longer absences from work after CMC I surgery [12-14], with, however, the time of sick leave also being shorter for patients after implant arthroplasty compared to RSI arthroplasty (4.7 vs. 8.9 months) [14]. Furthermore, the clinical and patient-reported outcomes in the short-term seem to be favourable for patients with a Touch® implant compared to RSI arthroplasty, once again undermining the potential of this specific implant.

Lastly, there is a risk that health insurances will not pay the Touch® implant, because it is more expensive than a RSI arthroplasty. However, if we could prove that other associated costs, such as loss of productivity, are significantly lower with the Touch® implant, we will have strong arguments against such decisions.

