4 PROJECT OBJECTIVES AND DESIGN

4.1 Overall objective

This prospective study intends to examine quality of life, costs and the cost-utility ratio from the health care system and societal perspectives at the Schulthess Klinik one year after surgery of the CMC I using the Touch® implant.

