The WPAI-SHP consists of 6 questions which allow to calculate the productivity losses caused by the specific health problem in the last seven days because of absenteeism (absence from work) and presenteeism (reduced productivity when at work). Consequences of the specific health problem on the ability to carry out regular daily activities, other than work, are also assessed. The WPAI-SHP was tested for validity and reliability for various disorders and can be easily adapted to a specific health problem by replacing the word "problem" by the name of the problem. In this study, we will also use the German and English version and insert the word "Daumenbeschwerden" or "thumb problems" at the appropriate places.

In addition to the WPAI-SHP, patients will be asked to report their current work status and income. Questions on current work status include 1) the number of hours usually worked in a week, 2) whether level of employment was reduced due to the health problem, 3) the duration of the absence from work after surgery and 4) current monthly personal income in brackets of 2'000 Swiss Francs (CHF) up to 16'000 CHF. The questions on personal income has been adapted from a previous population based survey on low back pain [27] and is similar to the question used in the Swiss Health Survey. The monetary value of productivity losses will be calculated by combining the WPAI-SHP with the questions on work status and income (www.reillyassociates.net).

Pricing, perspective and discounting

We will present direct and indirect medical costs in Swiss Francs. We will choose the hospital and the social perspective. Thus, our results can primarily inform decision makers within the hospital and local authorities about the costs of service provision and health related costs for society. Costs will not be discounted due to the short time frame. Current standards for performing health economic evaluations are applied [28].

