10.4.2 Primary Analysis

Quality of life

The EQ-5D-5L responses will be converted into utilities ranging from -0.66 (lowest QoL) to 1(highest QoL) according to the German value set [34]. The change in quality of life measured by the EQ-5D utility index from before to 1 year after surgery will be analysed by the paired t-test. Sample size will be sufficient to waive the requirement for Normal distribution of the outcome parameter.

Only one look at the data will be performed at the end of follow-up and significance level will be set at 5%.

Cost-utility analysis / Quality-Adjusted Life Years (QALYs)

A population preference-based value index from Germany will be used to calculate Quality-Adjusted Life Years (QALYs) for each patient. The gain in QALYs of Touch patients compared to RSI patients will be evaluated.

QALYs will be calculated as "utilities" multiplied with "time units" under this utility. Then, a cost-utilityratio will be calculated as: Additional costs per additional QALY (Quality adjusted life year). The incremental cost-utility ratio will be calculated as the difference in costs over the difference in Quality-Adjusted Life Years (QALYs) between both interventions [28].

> Cost _{Touch®} - Cost _{RSI} Arthroplastik QALYS_{Touch®} - QALYS_{RSI} Arthroplastik

Sensitivity analyses will be performed considering:

- Different assumptions of gain in QALYs
- Different assumptions for calculation of indirect costs (productivity losses)
- Different assumptions about the direct medical costs.

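### The primary hypothesis turns on an acceptable ICER, but no threshold is adopted, no stated analysis tests it, and the cost perspectives differ between sections

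*Protocol*

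**What the plan says.** Protocol 10.1 sets up a formal null and alternative. The alternative is that Touch "is more cost-effective than the RSI arthroplasty in terms of an acceptable ICER"; the primary objective (4.2) and primary outcome (5.1) use the same notion of acceptability.

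On what counts as acceptable, section 3.1 says "There is no explicit threshold defining a cost-effective intervention" and then, as background, "Thresholds have been suggested being below 50'000 USD - 150'000 USD for high-income countries". Section 10 does not take up any value from that range. Section 5.1 adds "We will present direct and indirect medical costs in Swiss Francs".

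On the analysis, 10.4.2 says "The incremental cost-utility ratio will be calculated as the difference in costs over the difference in Quality-Adjusted Life Years (QALYs) between both interventions". Sensitivity analyses vary the assumptions on QALY gain, productivity losses and direct costs. The one significance test named there concerns the change in utility "from before to 1 year after surgery will be analysed by the paired t-test", at a 5% level.

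On perspective, 4.1 speaks of evaluating cost-utility "from the health care system and societal perspectives", while 5.1 says "We will choose the hospital and the social perspective".

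**The concern.** A hypothesis needs a condition under which it is true and an analysis that can decide it. Here the condition contains an undefined word. The planned quantity is a single ratio, and the named test compares Touch patients with themselves before surgery, so it says nothing about Touch against RSI on cost-effectiveness. The scenario runs change assumptions; they do not describe sampling error.

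A ratio is also a poor decision quantity in its own right, because its sign does not say which treatment is better. A negative value arises when Touch saves money and gains QALYs, and equally when it costs more and loses QALYs.

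What is at stake is that the threshold could be picked after the result is known. The manufacturer part-funds the study (2.5, 13.1), and 3.1 states that the results are meant to supply arguments towards insurers. A conclusion that depends on a later choice of threshold would serve that purpose badly.

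**Working it through.** **Inputs.** From 10.2: RSI n = 42, mean 0.91, SD 0.09; Touch n = 68, mean 0.96, SD 0.05; two-sided alpha 0.05; power 0.90; dropout 15%. From 3.1: 50,000 to 150,000 USD. The Protocol gives no cost difference and no cost SD.

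**1. The plan's own figure.** With 42 controls and the Satterthwaite t-test, the smallest Touch group reaching 90% power for a difference of 0.05 is 68 (power 0.9003), and 68/0.85 = 80. The sample size reproduces. It powers the between-group difference in 1-year utility, not the hypothesis in 10.1.

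**2. What the open threshold does.** The largest acceptable extra cost is threshold × QALY difference. *Assumptions:* the utility difference is held for a full year, so that it equals the QALY difference, and the thresholds are taken at face value in the cost currency. Smaller gains are shown for range.

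| QALY difference | at 50,000 | at 100,000 | at 150,000 |
|---|---|---|---|
| 0.05 | 2,500 | 5,000 | 7,500 |
| 0.025 | 1,250 | 2,500 | 3,750 |
| 0.01 | 500 | 1,000 | 1,500 |

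At 0.05, any extra cost between 2,500 and 7,500 passes or fails by the choice of threshold alone. A fixed exchange rate would rescale all the limits but leave the threefold spread.

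**3. The ratio as a decision quantity.** Let ΔC and ΔQ be the cost and QALY differences (Touch minus RSI) and λ the threshold. Net monetary benefit is NMB = λΔQ − ΔC, and Touch is cost-effective when NMB > 0. If ΔQ > 0, then ΔC/ΔQ < λ is the same condition. If ΔQ < 0, multiplying through by ΔQ flips the inequality, so ΔC/ΔQ < λ means NMB < 0: the verdict is reversed. Illustrative values at λ = 50,000:

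| ΔC | ΔQ | ICER | ICER < λ | NMB |
|---|---|---|---|---|
| +2,000 | +0.05 | 40,000 | yes | +500 |
| −2,000 | +0.05 | −40,000 | yes | +4,500 |
| +2,000 | −0.05 | −40,000 | yes | −4,500 |
| −2,000 | −0.05 | 40,000 | yes | −500 |
| −8,000 | −0.05 | 160,000 | no | +5,500 |

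The last three rows are decided wrongly.

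**4. How likely a negative estimate is.** *Assumption:* the 1-year utility SDs stand in for QALY SDs, with a normal approximation. SE = √(0.09²/42 + 0.05²/68) = √(0.00019286 + 0.00003676) = 0.0152. The chance that the estimate falls below zero is Φ(−true gain/SE):

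- true gain 0.05: Φ(−3.30), about 0.05%
- true gain 0.025: Φ(−1.65), about 5%
- true gain 0.01: Φ(−0.66), about 25%

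**5. Perspectives side by side.** The societal element is common to 4.1 and 5.1. The other one is the health care system in 4.1 and the hospital in 5.1, which are different cost boundaries. Sections 4.2 and 5.1 build the ICER from direct medical plus productivity costs, which is in effect societal, but no perspective is labelled as the base case.

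**The case against.** The strongest defence has four parts.

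- **The threshold rule is inferred.** The Protocol never writes that the ICER must lie below a threshold; it says only acceptable, and 5.1 says that current standards for economic evaluation are applied. This stands: the reversal in step 3 concerns the natural reading, not a stated rule. At the planned gain of 0.05 it is also remote. A reader might infer that the plan as written goes wrong in two of the four cost-effect quadrants; the document does not support that.
- **Uncertainty methods may be in an analysis plan that is not shown.** This also stands. The absence of a bootstrap, a cost-effectiveness plane or an acceptability curve from the Protocol is not the defect, and one cannot say that no analysis anywhere could decide the hypothesis. The undefined term, however, is inside the Protocol's own hypotheses, and the test the Protocol does name cannot decide them.
- **The sign of the net cost difference is open.** A reader might infer that the sponsor expects a negative ICER, since 3.1 hopes for earlier return to work and better outcomes. But 3.1 also calls the implant more expensive, and 4.3 asks whether direct costs are higher. No expected net sign is stated.
- **The perspective conflict is limited.** Societal and social mean the same thing, and the cost components of the ICER are listed consistently. Only the second perspective and the missing base-case label need attention.

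In mitigation, 2.5 keeps the principal investigator out of the data analysis and gives the clinic ownership of the data and freedom to publish. That reduces the worry about influence, but it does not fix the threshold.

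**Conclusion.** The point holds. The primary hypothesis depends on a value that the Protocol does not adopt. The only figures cited span a factor of three in a different currency from the costs, and no analysis stated in the Protocol tests the null.

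The size given is an illustration: a band of extra cost from 2,500 to 7,500 in which the answer depends on a later choice. It rests on a 0.05 utility difference lasting a full year and on thresholds at face value in francs. Neither comes from the Protocol, which defines QALYs as utility multiplied by time and measures utility at five time points.

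The weakness of the ratio is secondary. It matters little if the true gain is 0.05, and more if the one-year QALY gain is 0.025 or 0.01. The mismatch in perspectives is a matter of reconciling 4.1 with 5.1, not evidence that the primary cost inputs are contradictory.

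**What to change.** 1. Restate the hypotheses in 10.1 as incremental net monetary benefit (threshold × QALY difference − cost difference) ≤ 0 against > 0. Use one threshold in CHF per QALY that the sponsor chooses and justifies before analysis. Use the two ends of the cited range, converted at a stated rate, as sensitivity analyses.
2. Name a bootstrap 95% confidence interval for net benefit as the test, rejecting the null if the lower limit is above zero. A simple patient-level bootstrap does not fit: control outcomes come from the earlier cohort of 42, while control direct costs come from other, concurrent RSI patients (Synopsis, 5.1, 8.1.2). Resample the Touch cohort, the RSI outcome cohort and the RSI cost cohort separately, or resample the RSI patients by matched pair, and say which.
3. Name the societal perspective, with direct medical plus productivity costs as 4.2 and 5.1 already list them, as the base case. Use the same second perspective in 4.1 and 5.1.
4. Report the ICER descriptively, always with its quadrant.

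The cost is an amendment to wording, some analysis work and a commitment in advance to one threshold and one perspective. No new data are needed. The sample size in 10.2 was not derived for net benefit, and without a cost SD its power for that test cannot be worked out from the Protocol; the amendment should say so.
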